### 7.13.2 Laboratory Data

Descriptive statistics of the observed values and change from baseline (continuous data) will be presented by treatment group and visit for each hematology (hemoglobin, hematocrit, red blood cell count, white blood cell (WBC) count (with differential [lymphocytes, neutrophils, eosinophils, basophils, and monocytes]), platelet count, hemoglobin A1c, activated partial thromboplastin time, prothrombin time and international normalization ratio), urinalysis (color, turbidity, specific gravity, pH, glucose, protein, ketones, urobilinogen, bilirubin, blood nitrate, leukocyte esterase, and microscopic examination) and serum chemistry (albumin, alanine aminotransferase [ALT], alkaline phosphatase, aspartate aminotransferase [AST], direct bilirubin, total bilirubin, blood urea nitrogen, calcium, chloride, creatine kinase, creatinine, gamma-glutamyl transferase, glucose, lactate dehydrogenase, potassium, sodium, uric acid) parameter. Each measurement (continuous data) will be classed as below, within, or above normal range, based on ranges supplied by the laboratory used. Laboratory data will be summarized for the secondary analysis period.

Shift tables in relation to the normal range from baseline to each follow-up visit will be presented.

All other laboratory tests will be listed only. This includes troponin I, troponin T, lipid panel, plasma cortisol, human immunodeficiency virus (HIV), hepatitis B, hepatitis C, and serum

pregnancy test (females of childbearing potential only), cortisol, urine drug screen, and urine pregnancy test.

A listing of abnormal laboratory measurements defined as any out of normal range laboratory values recorded throughout the study will be presented.

### 7.13.3 Vital Signs

Descriptive statistics for observed values and changes from baseline in the following vital signs will be presented by treatment group, visit, and timepoint within visit:

- Systolic blood pressure (mmHg)
- Diastolic blood pressure (mmHg)
- Pulse rate (Heart Rate) [bpm]

Vital signs data will be summarized separately for both the primary and the secondary analysis periods. Vital sign values will be categorized into the following potential clinical concern categories if applicable, and then summarized.

[figure not shown]
Vital Sign	Potential Clinical Concern Categories
Systolic blood pressure	$\geq 160$ mmHg
Diastolic blood pressure	$\geq 100$ mmHg
Pulse rate (Heart Rate)	$< 60$ or $> 100$ bpm

All vital sign measurements including the position of the subject when the measurement was taken will be listed.

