[REDACTED] Eligible subjects will then be randomly assigned (in a 1:1 ratio) on D1 to receive a single dose of an SP-102 TF, or placebo [REDACTED] in the vicinity of the epidural space or [REDACTED] under fluoroscopic guidance (for instructions on study drug injection see [Appendix D](#)). This first injection is referred to as the “index injection”. An appropriately trained physician, hereafter called the Injection Physician, administering the DB investigational product (IP) and other assisting staff (eg, nurse) will, therefore, not be blinded to the treatment assignment, while the rest of study staff involved in assessments and collection of data will remain blinded. Procedures will be in place at each site to ensure blinding, minimizing personnel involved with injection, and guarantee sequestration of imaging data acquired at the time of injection.

Fluoroscopic imaging guidance is required by this protocol to ensure proper placement of the injection needle (see instructions in [Appendix D](#)). Long-term persistent AEs are rarely seen with fluoroscopically-guided lumbosacral TF injections, however immediate and delayed AEs may include vasovagal episodes, procedure interruption from intravascular flow, pain exacerbation, injection site soreness, headache, and insomnia ([Plastaras-2015](#)). Avoidance of risk of procedural AEs in the placebo group by implementing an [REDACTED]

[REDACTED] is consistent with ethical considerations and use of [REDACTED] in interventional/surgical clinical trials (Wartolowska-2014). In addition to safety considerations and lowering the risk of procedural complication in the control group, the choice of an [REDACTED]

The choice of the TF injection approach with direct deposition of drug near the ventral epidural space at the affected level is selected based on published reviews documenting better effectiveness as compared to other approaches. For lumbar disc herniation with unilateral symptoms, the evidence for analgesic effect and ability to prevent surgery is greater for TF epidural injections as compared to caudal or interlaminar approaches (Manchikanti-2012; Cohen-2013).

[figure not shown]

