3.5.7 Safety Assessments

3.5.7.1 Physical Examination:

A complete physical examination, including examination of general appearance, skin, neck, eyes, ears, nose, throat, heart, lungs, abdomen, lymph nodes, extremities, and musculoskeletal system, will be performed at Screening. Specific musculoskeletal examination focusing on lumbar spine and lower extremities to exclude musculoskeletal sources of the predominant pain, such as SI joints and trigger points, will be performed in standardized manner and recorded. Height (in inches without shoes) and weight (in pounds) will be recorded at Screening.

3.5.7.2 General Neurological and Targeted Neurological Examinations:

A general neurological examination will include evaluation of mental status (awareness of person, place, and time), cranial nerves, motor function and balance, sensory exam (ability to feel) and reflexes. A targeted neurological examination demonstrating findings of, focusing on signs and symptoms of lumbosacral radiculopathy, including straight leg raise test, will be performed according to the checklist (see [Appendix A](#)). Both general and targeted neurological exams are to be performed by the same trained clinician throughout the study, if possible. Training for conducting examination will be available on video. General and targeted neurological examinations will be performed at Screening, Baseline (D1), W2, W4, W12, and W24, as well as if the repeat injection is administered.

The blinded Investigator will summarize and document the MRI findings based on the Lumbar Disc Nomenclature, the clinical presentation, and the Injection Plan in the eCRF prior to Baseline (D1).

3.5.7.3 Vital Signs and Body Weight:

Vital signs will include systolic and diastolic BP and heart rate. During the usual clinic visits, the subject is to be seated for approximately 3 mins before vital signs are recorded. During the injection procedure, the vital signs will need to be collected while the subject is in prone position on the fluoroscopy table ([Appendix D](#)). Vital signs will be recorded at each clinic visit.

3.5.7.4 Electrocardiogram:

Standard 12-lead ECGs will be measured on the site machines at Screening. The ECG results will be documented in the eCRF.

3.5.7.5 Laboratory Parameters:

The following clinical laboratory tests are to be performed at Screening and W24 unless noted below:

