5.2.9.4 Vital Signs

Summary statistics for the absolute vital sign value and the changes from baseline will be presented by treatment group for each visit, for each of the following vital signs:

- Systolic blood pressure (mmHg)
- Diastolic blood pressure (mmHg)
- Heart rate (bpm)

Vital sign values will be categorized into the following potential clinical concern categories if applicable and summarized.

Vital Sign	Potential Clinical Concern Categories
Systolic blood pressure	≥ 160 mmHg
Diastolic blood pressure	≥ 100 mmHg
Heart rate	< 60 or > 100 bpm

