#### 7.4 Conventions

All data listings, summaries, figures and statistical analyses will be generated using SAS version 9.4 or higher.

Subjects will be randomized to 1 of 2 treatment groups (SP-102 or placebo) and will receive 1 injection at Baseline (D1). After 4 weeks, an additional injection of SP-102 may be administered to all subjects regardless of the treatment they were originally randomized to. Because of this, baseline, efficacy, and safety variables will be summarized in two ways.

The first will summarize data for the 2 randomized treatment groups for the primary analysis period. Subjects will be analyzed in either the SP-102 or placebo treatment groups. Baseline summaries and data for this first 4 weeks will be summarized using the following treatment columns. Only baseline data will have the overall column.

SP-102	Placebo	Overall
--------	---------	---------

The second will classify subjects into 1 of 4 groups and will summarize data for the secondary analysis period. These 4 groups include the following:

- Subjects who receive only 1 SP-102 injection
- Subjects who receive 2 SP-102 injections

- Subjects who receive only 1 placebo injection
- Subjects who receive 1 placebo injection and 1 SP-102 injection

The 4 treatment groups will be used in the summary and analyses involving the secondary analysis period (randomization through end of study).

These 4 groups may be combined for additional analyses (eg, combine into one group any subject who received an injection of SP-102 at any point in time).

[REDACTED]

SP-102/SP-102	PBO/SP-102	SP-102/none	PBO/none	Overall
---------------	------------	-------------	----------	---------

Overall columns are to be included within the table shells as follows:

Data	Column labels
Demography	Treatment and overall
Baseline	Treatment and overall
Disposition	Treatment and overall
Prior Medications	Treatment and overall
Concomitant Medications	Treatment and overall
Efficacy	Treatment
AEs	Treatment
Other safety	Treatment

Listings will be sorted in the following order: treatment group, subject, parameter, and visit unless otherwise stated. All data will be listed. Subjects who were not randomized will be displayed after the randomized treatment groups.

Continuous variables will be summarized by the number of non-missing observations, mean, median, standard deviation, and minimum and maximum. For all tabulations of changes from

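### The vital-sign concern categories have no low side for blood pressure and do not separate new from pre-existing values, so subjects with low pressure or a marked fall are not counted by arm

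*SAP*

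**What the plan says.** The protocol (5.2.9.4) states: "Vital sign values will be categorized into the following potential clinical concern categories if applicable and summarized". The SAP (7.13.3) repeats this almost word for word: "Vital sign values will be categorized into the following potential clinical concern categories if applicable, and then summarized". Both documents then give the same three rows. Systolic and diastolic pressure each have an upper limit only. Heart rate has both limits, "< 60 or > 100 bpm".

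Two other places in the protocol bear on this. Section 3.1, on fluoroscopically guided transforaminal injection, says that "immediate and delayed AEs may include vasovagal episodes". Section 3.5.7.3 arranges for measurement at the relevant time: "During the injection procedure, the vital signs will need to be collected while the subject is in prone position on the fluoroscopy table".

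The SAP plans further vital-sign output. Descriptive statistics for observed values and changes from baseline "will be presented by treatment group, visit, and timepoint within visit", and SAP 7.4 defines the continuous summary to include "mean, median, standard deviation, and minimum and maximum". All readings are listed with the subject's position. SAP 7.3.8 limits the tables to scheduled post-baseline values, except at repeat-injection visits; other unscheduled readings are listed only.

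**The concern.** At the index injection only the SP-102 arm has the transforaminal procedure; the control is an intramuscular injection, chosen partly to spare that arm procedural risk. The arms therefore differ by design in exposure to the reactions that protocol 3.1 names, and a safety reader will want to know how many subjects in each arm had a low pressure or a marked fall around the injection. That a vasovagal reaction lowers blood pressure is general medical knowledge; the documents do not say it.

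The table of outlying vital signs is the natural place for that count, and its blood-pressure rows cannot supply it. The plan gives no reason for treating blood pressure differently from heart rate in the same table, or from laboratory values. SAP 7.13.2 classes continuous laboratory values as low, normal or high and adds shift tables from baseline.

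**Working it through.** The plan states no figure to reproduce, so the check sets the passages side by side.

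**1. Category limits (SAP 7.13.3 and protocol 5.2.9.4, identical).**

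| Vital sign | Low side | High side |
|---|---|---|
| Systolic | none | ≥ 160 mmHg |
| Diastolic | none | ≥ 100 mmHg |
| Heart rate | < 60 bpm | > 100 bpm |

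A systolic value below 160 mmHg with a diastolic value below 100 mmHg meets no blood-pressure category, however low it is. A subject who drops from 160 mmHg or more to a low systolic value simply leaves the category. A slow pulse in the same episode can be flagged.

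**2. Reference to the pre-injection value.** The categories apply to each value on its own. By the printed text, a subject at or above 160 mmHg before and after injection is in the post-injection category just as a new case would be. The list of tables is redacted, so whether the layout shows baseline alongside cannot be checked.

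**3. What the other outputs supply.**

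- *Minimum and change from baseline.* These show the most extreme reading in each group at each timepoint, but not how many subjects had one.
- *Baseline.* SAP 7.3.2 uses the last value before the first injection. At the index visit, change from baseline is therefore change from pre-injection. At a repeat injection 4 to 20 weeks later, it is not change from that day's pre-injection value.
- *Position.* Protocol 3.5.7.3 has usual clinic readings taken seated and injection readings taken prone, so a change may mix the two.
- *Unscheduled readings.* Under SAP 7.3.8, an extra reading taken because a subject felt unwell at the index visit, if recorded as unscheduled, is listed but does not reach the tabulated minimum.
- *Adverse events.* SAP 7.13.1 counts procedure-related events by preferred term. This needs someone to report an event. Protocol 4.1.4 says when an abnormal laboratory value is recorded as an adverse event; the visible text has no such rule for vital signs.
- *Listings.* These are complete, but the reader must do the counting.

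**4. Size.** About 400 subjects are randomized 1:1, so 400 / 2 = 200 per arm and about 200 have the transforaminal procedure at the index injection. The documents give neither a rate of vasovagal episodes nor a size of pressure fall, so the number of subjects missing from the table cannot be estimated from them.

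**The case against.** The strongest reply is that the protocol itself calls vasovagal episodes adverse events, and that the SAP tabulates procedure-related adverse events with incidence and number of events. A threshold table is only a supplement. Protocol and SAP also agree exactly, nothing is unexecutable, and no test, estimate or error rate depends on these rows. All of that stands, and it is why the point is minor. What it leaves open is a count based on measured readings that does not depend on event reporting. That has some value here because the staff at the injection know the treatment (protocol 3.4.2).

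A second reply is that low-pressure rows alone might miss their target, because SAP 7.3.8 would keep unscheduled index-day readings out of them. This is correct, and the fix has to deal with it.

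A reader might go further and infer that low pressures would go unreported. The documents do not support that: the tabulated minimum, the change from baseline by timepoint, the full listing and the adverse-event tables can all show them, and a pulse below 60 bpm is flagged. Nor do they support the inference that long-standing hypertension will dominate the table. They give no baseline rate, some exclusion criteria are redacted, and randomization would be expected to balance prior hypertension in the two-group comparison. Section 3.1 names vasovagal episodes as one of several possible events and does not rank them as the main one.

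**Conclusion.** The point holds in a limited form. The concern categories are one-sided for blood pressure and two-sided for heart rate, with no stated reason, and as printed they do not separate values that are new after injection from those already present. The plan therefore gives no count by arm of subjects with low pressure or a marked fall, in a comparison where one arm alone has the transforaminal procedure at the index injection.

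This is a minor improvement to safety reporting. Efficacy inference, sample size and error rates are untouched. The conclusion about the categories rests on the printed limits, which match in both documents. Its relevance rests on one assumption from outside the documents, that vasovagal reactions can lower blood pressure. The redacted table list, the redacted schedule of assessments and the unseen injection instructions might contain a finer display; if so, SAP 7.13.3 need only refer to it.

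**What to change.** In SAP 7.13.3:

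- Add a low systolic and a low diastolic display category, and a category for a fall from the same-day pre-injection reading, applied at the index and the repeat injection. The sponsor's medical lead should set the cut-offs, stated to be display thresholds only and not rules for managing subjects. No values are proposed here.
- In every category, count subjects who were not already in it before injection.
- Include unscheduled readings from the injection day in these rows, as a stated exception to SAP 7.3.8. Show how many subjects enter only through such a reading, because extra readings are likelier in subjects with symptoms.
- Record the change in SAP section 11, since protocol 5.2.9.4 has the one-sided categories.

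If the sponsor prefers upper limits only, one sentence giving the reason would do. The cost is SAP wording and a few descriptive table rows, programmed from data already collected.

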### 7.13.4 Electrocardiogram Data

Descriptive statistics for observed values in the following ECG variables at the screening visit will be tabulated:

- Pulse Rate (Heart rate) [bpm]
- PR interval (ms)
- RR interval (ms)
- QRS duration (ms)
- QT interval (ms)
- QTc interval (ms) [Bazett's formula - QTcB]
- QTc interval (ms) [Fridericia's formula - QTcF]

All ECG measurements and the position of the subject when the measurement was taken will be listed.

### **7.13.5 Physical Examination**

The body systems within the physical examination data at Screening will be summarized by treatment group and finding (Normal, Abnormal NCS, Abnormal CS). Details of clinically significant findings will be listed.

### **7.13.6 Neurological Examination**

Neurological examination will include evaluation of mental status (awareness of person, place, and time), cranial nerves, motor function and balance, sensory exam (ability to feel) and reflexes. Specific neurological examination demonstrating findings of radiculopathy, including straight leg raise test will be performed as part of this evaluation, according to the checklist (see Appendix A of the protocol).

Shift tables in relation to finding (Normal, Abnormal) from baseline to each follow-up visit will be presented for the General Neurological Exam results. Details of any abnormalities will be listed.

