#### 3.2 Secondary Objectives

The secondary objectives of the study are to:

- Evaluate degree of disability over time as measured by the Oswestry Disability Index (ODI).
- Characterize the change of the subject's radiculopathy symptoms and overall condition using PainDETECT, Brief Pain Inventory-Short Form (BPI-SF), Clinical Global Impression of Change (CGIC), and Patient Global Impression of Change (PGIC).
- Evaluate the safety of a single and repeat SP-102 TF injection.

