#### 4.4 Safety Endpoints

- Adverse Events
- Change from Baseline (D1) in laboratory parameters
- Change from Baseline (D1) in vital signs
- Change from Baseline (D1) in neurological examination

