#### 7.3.2 Baseline

Except otherwise specified, baseline is defined as the last non-missing value (either scheduled, unscheduled or repeat) before the subject receives the first dose of SP-102 TF or placebo injection on D1. Baseline calculations for variables collected in the diary are described in the efficacy analyses section.

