### 7.13 Safety Analyses

The safety analyses will be presented in two ways:

- 1) by the two treatment groups received in the first four weeks for the primary analysis period
- 2) by the four treatment groups for the data up to 24 weeks for the secondary analysis period

All safety analyses will be done in the Safety Analysis Population.

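### Neurological shifts and vital-sign changes after the repeat injection are referred to the pre-index value, so the tables do not show the change from before to after the repeat

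*SAP*

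**What the plan says.** The SAP's secondary objectives include: "Evaluate the safety of a single and repeat SP-102 TF injection". Both safety endpoints at issue are anchored to Day 1 in SAP 4.4: "Change from Baseline (D1) in neurological examination" and "Change from Baseline (D1) in vital signs".

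SAP 7.3.2 gives the general rule: "baseline is defined as the last non-missing value (either scheduled, unscheduled or repeat) before the subject receives the first dose". It allows exceptions where they are stated. SAP 7.13.3 and 7.13.6 state none.

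- **Neurological exam (SAP 7.13.6):** "Shift tables in relation to finding (Normal, Abnormal) from baseline to each follow-up visit will be presented", for the General exam only. Details of abnormalities are also listed.
- **Vital signs (SAP 7.13.3):** "Descriptive statistics for observed values and changes from baseline in the following vital signs will be presented by treatment group, visit, and timepoint within visit". The section adds absolute concern categories and a listing that includes position.
- **Grouping (SAP 7.13):** besides the two-group display for the first four weeks, safety is shown "by the four treatment groups for the data up to 24 weeks for the secondary analysis period". SAP 7.4 defines those groups by index treatment and by whether a repeat was received.
- **Adverse events (SAP 7.13.1):** treatment-emergent events are summarised separately before and after the second injection. No such split is written for the neurological exam or vital signs.

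The data needed for a pre/post comparison are planned. Protocol 3.5.7.2 schedules neurological exams at Screening, D1, W2, W4, W12 and W24, "as well as if the repeat injection is administered". Protocol 3.5.7.3 takes vital signs at every clinic visit, and Protocol 3.1 adds a visit 14 days after the repeat. SAP 7.3.8 keeps repeat-visit assessments in the analysis. It does not say which table row they occupy, and it does not mention the 14-day visit.

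**The concern.** The repeat is a second transforaminal injection, and for subjects who had placebo first it is their first exposure to SP-102. Its safety is a stated objective, and Protocol 1.8 describes serious neurologic events as the class risk. The natural summary for exam findings and vital signs is the change from just before that injection to just after it. The readable SAP text gives the change from Day 1 instead, up to 20 weeks before the repeat, under a column label fixed by whether a repeat was ever given. A within-subject change at the repeat can then be tabulated as no change, a change that preceded the repeat can sit in a repeat column, and some rows combine subjects on both sides of their repeat.

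**Working it through.** The plan states no figure on this point, so there is none to reproduce. The check has three parts.

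**1. What the D1-referenced shift table records (General exam)**

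| D1 | Last exam before repeat | Exam after repeat | Shift from D1 | Shift from pre-repeat exam |
|---|---|---|---|---|
| Abnormal | Normal | Abnormal | Abnormal to Abnormal | Normal to Abnormal |
| Normal | Abnormal | Abnormal | Normal to Abnormal | Abnormal to Abnormal |
| Normal | Normal | Abnormal | Normal to Abnormal | Normal to Abnormal |

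Row 1 is a deterioration after the repeat shown as no shift. Row 2, in a subject who had placebo first, is a pre-repeat change shown as a shift in the PBO/SP-102 column. Only row 3 reads the same either way. An earlier visit row would count the row 1 subject as Abnormal to Normal, but separate visit tables do not link the two results within a subject.

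**2. Which rows mix pre- and post-repeat data**

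Inputs: repeat window W4 to W20 (Protocol 3.1) and the assessment schedules above.

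- Neurological exam (W2, W4, W12, W24): W2 is wholly pre-repeat, W4 essentially so, and W24 wholly post-repeat for recipients. W12 is the mixed calendar visit.
- Vital signs (every clinic visit): W8, W12 and W16 are mixed. W20 depends on same-day timing, and W24 is wholly post-repeat.

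The documents give no timing distribution. Let x = (w − 4)/16 be the fraction of the window elapsed at week w. The share of eventual recipients still pre-repeat is 1 − x for uniform timing, (1 − x)³ for an assumed early pattern, Beta(1,3), and 1 − x³ for an assumed late pattern, Beta(3,1).

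| Visit | x | Uniform | Early | Late |
|---|---|---|---|---|
| W8 (vital signs only) | 0.25 | 75% | 42% | 98% |
| W12 | 0.50 | 50% | 12.5% | 87.5% |
| W16 (vital signs only) | 0.75 | 25% | 2% | 58% |

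**3. Share of post-repeat Normal-to-Abnormal deteriorations shown as no shift**

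Let p be the share abnormal at D1, r the share of those normal again before the repeat, and q the share of D1-normal subjects abnormal before the repeat. Assume the same risk of deterioration after the repeat for everyone normal just before it. The share is then

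p·r / [p·r + (1 − p)(1 − q)].

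- p = 0.2, r = 0.2, q = 0: 0.04/(0.04 + 0.80) = 5%.
- p = 0.5, r = 0.2, q = 0: 0.10/(0.10 + 0.50) = 17%.
- p = 0.8, r = 0.5, q = 0.1: 0.40/(0.40 + 0.18) = 69%.

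All three inputs are assumptions. The spread shows that the documents do not determine the size. With a pre-repeat baseline and rows counted from the repeat, both the mixed share and the hidden share are zero by construction.

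**The case against.** The strongest case against is that serious harm would be found by other routes. SAP 7.13.6 lists details of abnormalities, and SAP 7.4 lists all data, so an abnormal-normal-abnormal sequence is visible for each subject. Treatment-emergent events are split at the second injection, with a rule assigning to SP-102 any placebo-period event that worsens after the repeat. Protocol 4.2.2 gives expedited handling to epidural infection or hematoma needing surgery and to paraplegia. This largely stands: a reader might infer that serious neurologic deficits would go unseen, and the documents do not support that. What remains is that a listing is not a summary. In addition, Protocol 4.2.1 counts signs present before treatment as adverse events only if they worsen, so a finding that resolves and returns to its D1 level may be counted nowhere.

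The second objection is that the argument does not carry over to vital signs. A reader might infer that a raised D1 reading hides an extreme value after the repeat. It does not, because SAP 7.13.3 also presents observed values and absolute concern categories. For vital signs the problem is limited to mixed rows and the D1 reference for changes.

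Third, much of the relevant text is redacted: the schedule of assessments, the repeat-visit procedures, part of SAP 7.4 and the lists of tables. Repeat-visit rows may exist, since SAP 7.3.8 retains those data and 7.13.3 uses timepoints within visits. A suitable table may exist too. The readable analysis text defines neither a pre-repeat comparator nor a row mapping.

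Finally, the SAP follows the protocol's own D1-anchored endpoints. That is true, but those tables do not give the pre- to post-repeat change for an objective that names the repeat.

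**Conclusion.** The point holds for the readable text. General-exam shifts and vital-sign changes are measured only from the pre-index value, in groups defined by whether a repeat was ever given, and they do not give the change across the repeat injection. Mixing affects W12 for the neurological exam and W8, W12 and W16 for vital signs.

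The size is unknown. The 50% still pre-repeat at W12 rests on uniform timing, and early clustering would lower it.

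Three further readings are not supported:

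- Mixing of neurological results at W8: no neurological exam is scheduled then.
- A large hidden share inferred from this being a radiculopathy population: the shift table covers the General exam, while the radiculopathy-focused signs belong to the Targeted exam (Protocol 3.5.7.2).
- Attribution of placebo-period changes to SP-102: PBO/SP-102 labels a treatment sequence, and a D1-referenced shift in that column is not itself an attribution, although it can be read as one.

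The primary efficacy analysis is unaffected. The change should be made because a stated rule can misclassify post-repeat change and the remedy is inexpensive.

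**What to change.** - **SAP 7.3.2:** add a second safety baseline for repeat recipients, the last non-missing assessment before the repeat injection. If the repeat-day exam is not done before injection, this definition falls back to the last earlier one.
- **SAP 7.13.6:** add a shift table from that baseline to each later exam, by index arm.
- **SAP 7.13.3:** add change from that baseline, by index arm, using readings in the same position. Protocol 3.5.7.3 has subjects seated at usual visits and prone during the injection procedure.
- **D1-referenced four-group tables:** show pre-repeat and post-repeat values separately, as SAP 7.13.1 does for adverse events.
- **SAP 7.3.8:** state how repeat-visit and 14-day post-repeat data map to table rows.

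Label the new tables descriptive and non-randomised. If the redacted lists already contain such tables, the text need only define their baseline and rows.

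The cost is SAP wording and a few extra tables from data already planned. The downside is that these are uncontrolled, open-label summaries. No dose, schedule or clinical rule changes, and the sample size is unaffected.
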